Protocol Title

High-Dose Vitamin D3 in the Treatment of Human Immune Deficiency Virus Patients, A Double-Blind Randomized Control Trial

Protocol Version: 1.0

Date: August 15, 2019

Institute of Social & Cultural Studies
University of the Punjab,
Lahore

Abstract

Human immunodeficiency virus is a key challenge for global health. Vitamin D deficiency is common in people living with HIV infection. Antiretroviral therapy may create unique risk factors for vitamin D insufficiency, including alterations of vitamin D metabolism by ART.

The objective of the study is, to know the effect of high dose Vitamin D, in the treatment of HIV patients with antiretroviral therapy. It will be a randomized controlled trial, in which 104 patients visiting Said Mitha Teaching Hospital Lahore will be included.

The patients will be divided into two groups. Group-A patients will receive ARV + Vitamin D supplements and patients in Group-B will receive only antiretroviral therapy and placebo.

Methods/design: A randomized placebo double blind control trials of patients with age 19-50 years will be the participants of our study at VCCT center of said Mitha Teaching Hospital, located in walled city of Lahore, Pakistan. Participants will be randomly allocated to receive 25 hydroxyvitamin D supplementation (n=) or placebo (n=) with the start of ART.

The primary outcome will be achieved with high dose of serum 25-hydroxyvitamin D level at 24 weeks. Secondary outcome will include decrease in viral load, increase mean CD4 count to reduce prevalence of clinical symptoms (elevated levels of LFTs, decrease HB level & serum calcium level). Purposive sampling will be carried out.

Data will be collected through Performa, which will be entered and statistically analyzed, using SPSS version 24.0, This Performa is designed by the Punjab AIDS Control Programme including socio-demographic information, Pretest

information, posttest information & follow up chart. Chi-square test will be used to estimate the association among qualitative variables.

Discussion: High dose Vitamin D supplementation in HIV-infected patients has not previously been investigated in Pakistan and it is unknown whether increasing levels is associated with improved clinical outcome or not. Therefore, it is significant to conduct a study to know the effect of vitamin D in the treatment of HIV patients with antiretroviral therapy.

From the public health point of view, it is also important to know the effectiveness of high dose of 25-hydroxy Vitamin-D level in positive human immune deficiency patients.

Trial Registration: The trial will be registered with clinical trials..

Keywords: AIDS, HIV, anti-retroviral therapy, high dose 25-hydroxy Vitamin-D level, CD4 count, viral load.

1. INTRODUCTION

1.1 Background

Human immunodeficiency virus (HIV) is retrovirus; it infects immune system cell and impairs their function. This virus causes infection that leads to worsening the immune system, resulting in immune deficiency. There are two types of HIV i.e. HIV 1 and HIV 2. HIV 1 is more virulent easily **transmit**. HIV in majority is caused by HIV 1 while HIV 2 is less easily transmitted and it is mostly confined to West Africa. HIV 2 is also called non-**progressive**, which means the chance of progression into AIDS is less (Nyamweya et al., 2013; Abbas, Naveed, Qamar, Zehra& Jawed, 2016).

Human immunodeficiency virus is a global health problem (Mansueto, Seidita, Vitale, Gangemi, Iaria&Cascio, 2015)and a major health concern which remains incurable (Imran, **Nasi&Riaz**, 2018). Globally, about 36.7 million people are living with HIV. HIV infection causes AIDS and is epidemic throughout the world. In 2016; about 1.8 million were reported as newly infected and 1 million died of AIDS-related illnesses in the same period (Khan, Wali, Fatima, Yaqoob& Aziz, 2019).

The HIV infection is becoming a prevalent disease in Pakistan, and its death toll has been steadily increasing each year since 1987 (Hussain et al., 2018).In Pakistan, HIV epidemic trend has increased from “low prevalence, high risk” to “concentrated” epidemic particularly in high risk populations. According to World Health Organization and National AIDS Control Program, an estimated 91,340 people were living with HIV in 2014. Majority of HIV-infected population belonged to high risk groups including

injection drug users (IUD), transgender, males and female sex workers. Also, the previous studies have shown prevalence rate of 27.2%, 5.2%, 1.6% and 0.6% respectively in these high risk groups (Shaukat et al., 2018).

1.2 Study Medication

The introduction of antiretroviral therapy (ART) has not only improved the prognosis of HIV patients by reducing their mortality and morbidity, but also has revealed some complications related to the therapy (Grana et al., 2019). Vitamin D deficiency is common in people living with HIV infection (Hileman, Overton&McComsey, 2016; Hsieh & Yin, 2018). HIV infection and exposure to certain anti-retroviral might contribute to altered levels of 25-hydroxy vitamin D **25(OH)D**. The preferred and most commonly used parameter for assessment of vitamin D status is serum 25(OH)D concentration. 25(OH)D, which is the major circulating metabolite of vitamin D and reflects the vitamin D inputs from cutaneous synthesis and dietary intake (Lips, 2010; Deshwal&Arora, 2019). Most current guidelines define vitamin D deficiency and insufficiency as a serum vitamin D value 25 (OH) D) <30 nmol/L (<12 ng/ml) and between 30–50 nmol/L respectively (12–20 ng/ml) (Penner et al., 2018). The prevalence of vitamin D deficiency in HIV infected individuals ranges from 60% to 90% and is associated with female gender, black ethnicity and antiretroviral use (Tiraboschi et al., 2016).

HIV infection may create unique risk factors for vitamin D insufficiency such as chronic inflammation, and both the protease inhibitor and non-nucleoside reverse transcriptase inhibitor classes of antiretroviral agents may enhance vitamin D metabolism via modulation of the cytochrome P450 system and vitamin D hydroxylation. Additionally, in HIV-infected persons, vitamin D insufficiency has been

associated with lower CD4+ T lymphocyte counts (Aziz et al., 2013; Coelho et al., 2015).

The main role of vitamin D is to maintain the function of monocytes and macrophages which are linked to human innate immunity to certain infectious agents. This role is very important in body's natural defense against infection in which macrophages play a vital role in pathogenesis. Vitamin D acts by combining the nuclei receptor on affected cells so both abnormality in receptor function and structure or low vitamin D level alter the immunity against HIV (Nnoaham & Clarke, 2008; Afzal, Rathore, Butt & Randhawa, 2018).

Vitamin D is obtained in its natural form by exposing the skin to sun rays that converts 7-dehydrocholesterol (pro-vitamin D3) into Cholecalciferol (vitamin D3) through which the bloodstream passes, where it joins the D-binding protein (VDBP) and is transported to the liver. The second source of vitamin D is via oral intake, through the transformation of ergosterol (vitamin D2) in plants and fungi. Vitamins D3 and D2 are both metabolized in the liver to 25-hydroxycholecalciferol and are transformed in kidneys into its active form, 1,25-dihydroxyvitamin D, which is a steroid hormone vital for calcium and bone metabolism (Conrado, de Barros Miranda-Filho & Bandeira, 2010).

1.3 Rationale for the Proposed Study

Human immunodeficiency virus is a leading health problem that exacerbates the quality of life and a major cause of mortality among patients. In Pakistan, HIV infection is also increasing rapidly while injection drug users, transgender and sex workers are high risk groups. Vitamin D deficiency is common in people living with HIV infection. It has recently been confirmed that Vitamin D supplementation reduces the progression of

disease and prevents HIV-infected individuals from mortality (Anderson et al., 2010; Mehta et al., 2010; Barbosa et al., 2014). Present study evaluates the effect of vitamin D in the treatment of HIV patients with antiretroviral therapy.

2. RESEARCH OBJECTIVE

2.1 Primary objectives:

1. To determine whether proposed oral high dose vitamin D3 is sufficient for achieving the physiological concentration in HIV positive patients on ART. (primary outcome)

2.2 Secondary objectives:

1. To determine whether this intervention also improves CD4 count, viral load count, liver enzyme in study participants. (Efficacy outcome).
2. To discover whether this interventional regimen is safe and well tolerated by study participants. (Safety outcome).
3. To ascertain socio-demographics factors responsible for decreased level of vitamin D3 in HIV positive patients on ART.

2.3 Tertiary objectives:

1. To conclude the effects of total leucocytes count in HIV patients with vitamin D supplementation.
2. To determine the effects of total neutrophil count in HIV patients with vitamin-D supplementation.
3. To investigate the effects of total basophil count in HIV patients with vitamin-D supplementation.
4. To determine the effects of total eosinophil count in HIV patients with vitamin-D supplementation.
5. To conclude the effects of total monocyte count in HIV patients with vitamin-D supplementation.
6. To establish the effects of total platelets count in HIV patients with vitamin-D supplementation.
7. To find out the effects of total hemoglobin count in HIV patients with vitamin-D supplementation.
8. To determine the effects of total lymphocytes count in HIV patients with vitamin-D supplementation.

3. Study Population

Patients who visited the VCCT center of GOVT Said Mitha Teaching Hospital Lahore and the treatment center of Jinnah hospital HIV clinic were the study population and they were HIV positive and on ART. The study population consisted of HIV patients ranging in age from 19 to 50 years. Patients with severe vitamin D3 deficiency were seen at the multi-centric outpatient HIV department.

3.1 Eligibility Criteria

Inclusion criteria:

- Age at enrolment between 19-50 years old
- Vitamin D deficiency level >20ng/ml
- Had not been taking any kind of vitamin D supplementation mega doses for since six months
- Written consent was signed by participants voluntarily

Exclusion criteria

- Pregnant women
- Vitamin D level <20ng/ml or taking vitamin D supplementation mega doses since last three months were not included

4. STUDY PROCEDURES

4.1 Study Population

Patients visiting Said Mitha Teaching Hospital Lahore will be the study population and having diagnosed with HIV positive patients.

4.2 Sampling technique:

Random list was generated for the double blind purpose. This list was generated through Excel sheet.

4.3 Ethical Consideration:

The study will be conducted after approval from the Punjab University Ethical Review Board. Permission will also be obtained from Punjab AIDS Control Programme to use health facilities and this study will be registered at Clinical Trial.gov, to use the health facilities and services of paramedics staff for data collection. Written consent of parents and guardians will be taken before starting the study.

4.4 Data Collection:

All staff involved in the study will be trained by the principal investigator before start of data collection. Trained laboratory technician will screen the patients aged 19 years to 50 years of age in (VDT) diagnostic center of hospital visiting outpatients department in their community and will refer the positive patients to treatment center of AIDS Control Programme clinic of Mayo Hospital Lahore, After receiving their prescribed ART, the two positive groups would be divided into two equal groups, one group will receive 25hydroxy vitamin –D and other halves will receive placebo at the same time once weekly for 12 weeks. Patients will be called for follow-up after every

4 weeks. At the end, we will perform posttest and check the level of 25 hydroxy in both groups and other parameters and by using logistic regression we will evaluate the results of effectiveness of 25 hydroxyin blood levels of HIV patients

4.5 Randomization:

The random allocation sequence will be generated in an excel spread sheet by a statistician who will be independent of the study. Consecutive numbers will be assigned to active vs. placebo in equal numbers. No restrictions (e.g. stratification, block size) will be applied. This sequence will be used by the study pharmacy to label pairs of syringes containing active and placebo medication with a study number assigned to active and placebo arms, respectively. These staff will assign the consecutive ID numbers to participants according to the sequence in which they are enrolled, and the hospital pharmacy then supply syringes of placebo active medication bearing this ID number.

4.6 Blinding:

Patients of all study participants will be blinded to allocation, as will be the doctors and the staff nurse who will enrol participants and perform study assessments. Active and placebo medication will be presented identically in 1 ml syringes, and will have identical appearance and texture.

4.7 Interventions:

All participants will be treated with vitamin D supplements (Annexure attached) provided by AIDS Control Programme at outpatients department according to WHO guidelines. Vitamin D and calcium will be supplied to HIV positive patients according to the study (Annexure attached) on a weekly basis by suitably trained staff

who will provide information regarding benefits of vitaminD advise as to how it should be taken. Participants who will be randomised to the intervention arm of the trial will receive one oral dose of 100,000 IU (10 mg) vitamin D3 (cholecalciferol) in 1 ml olive oil, will administer via a syringe at 5 and 12 weeks' post-initiation of vitamin D3 supplementation. Participants who will randomised to the control arm of the trial will receive one oral dose of placebo (1 ml extra virgin) via a syringe at 5 and 12 week's post-initiation of vitamin D3 supplementation. After screening further dose of RDA Vitamin-D will be provided for next 5 weeks to complete 24 weeks of study.

5. LAB ANALYSIS AND COLLECTION OF BLOOD SAMPLE:

25-hydroxyvitamin D concentration will be measured 0 and 60 days to assess baseline deficiency and then effect of supplementation, 3ml blood sample will be taken in gel tube after clot formation will be centrifuged. Serum or plasma may be stored for up to 3 days at 2-8 centigrade. Initially **Alere** HIV combo strips will be used for screening of HIV and syphilis, then on positive result we will use second screening on uni-gold HIV strip. Then on third step we will use SD HIV 1/2 3.0 strip for final confirmation of screening step and finally we perform RT-PCR at last.

The haemoglobin level will be determined at 0 days and 60 days to assess the anaemia and effect of supplementation in all selected participants. Blood sample will be drawn from patients who will give their consent voluntarily.

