6. STUDY SCHEDULE

Schedule of clinical assessment and procedure:

	Screening	Treatments			
	V 1 Screening & Assessment	V 2 Randomization & 1 st Dose	V 3 2 nd dose	V 4 3 rd dose	V 5 Post Assesments
	-7~1	1 Day	5 week	12 week	24 week
ICF	×				
Eligibility Criteria	×	×			
Baseline Questionnaire	×				
Weight	×		×	×	×
Height	×		×	×	×
Vital Signs	×	×	×	×	×
Vit-D	×			×	
				V4+1 Day	
CD4 count	×			×	
				V4+1 Day	
Viral load	×			×	
				V4+1 Day	
PCR	×			×	
				V4+1 Day	
CBC	×			×	
				V4+1 Day	
Study Medication		×	×	×	
AE Monitoring		×	×	×	×
RDA					×
End of Study					×

6.1 STUDY PROCEDURES AND ASSESSMENTS:

Visit Schedule:

Visit 1 (Screening, Days -3 to 1)

Subjects who were informed about the study and voluntarily gave written consent to participation had the following tests.

- a. Informed consent and screening number assignment
- b. Demographics

- c. Information on exposure to HIV infection
- d. Medical history
- e. Previous HIV lab test if any
- f. RT-PCR
- g. Laboratory tests
- h. Prior medications and therapies
- i. Physical examination (investigator questioning)
- j. Symptoms
- k. Body weight measurement
- l. Assessment of the inclusion/exclusion criteria

Visit 2 (Randomization, Baseline, Day 1):

- a. Medical history
- b. Prior medications and therapies
- c. Physical examination (investigator questioning)
- d. RT-PCR
- e. Laboratory tests
- f. Symptoms
- g. Assessment of the inclusion/exclusion criteria
- h. Randomization
- i. Prescription of test drug or placebo

Visit 3 (Day 4)

- a. Concomitant medications and therapies
- b. Physical examination (investigator questioning)
- c. RT-PCR
- d. Symptoms

e. Treatment adherence.

Visit 4 (Day 7):

a. Concomitant medications and therapies

b. Physical examination (investigator questioning)

c. RT-PCR

d. Laboratory tests

e. Symptoms

Visit 5 (Day 14)

a. Concomitant medications and therapies

b. Physical examination (investigator questioning)

c. RT-PCR

d. Laboratory tests

e. Symptoms

f. Body weight measurement

g. Adverse events

Visit 6 (Day 28):

a. Physical examination (investigator questioning)

b. Laboratory tests

c. AEs

d. Collection of clinical treatment information

Even if a subject was withdrawn, unless the subject withdrew the consent for safety follow-up, the safety follow-up was conducted at the scheduled visits (Visits 3, 4, 5, and 6) to collect the following clinical treatment information.

e. Treatment adherence

Unscheduled Visit:

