7.1 Primary outcome

The primary outcome analysis will be performed to check the difference change in Placebo group and Active Treatment group (Vitamin-D Group) through comparing mean difference from Visit 1 to Visit 4. This test will identify the mean increase or decrease in the Vitamin-D levels in the study Participants.

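### Protocol 4.7 states the vitamin D3 dose in two units that differ four-fold, and the weekly dosing in Protocol 4.4 conflicts with the three doses in both schedule tables

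*Protocol*

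**What the plan says.** **Strength.** Protocol 4.7 states that intervention participants "will receive one oral dose of 100,000 IU (10 mg) vitamin D3 (cholecalciferol) in 1 ml olive oil". No other section of the Protocol or SAP gives a number for the study dose. The SAP has none, the RDA supplement has no amount, and the only other IU figure is in the title of a cited study.

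**Frequency.** Protocol 4.4 says that one half receives the active product and that the "other halves will receive placebo at the same time once weekly for 12 weeks". Protocol 4.7 places doses at weeks 5 and 12 "post-initiation of vitamin D3 supplementation". The schedule tables in Protocol section 6 and SAP section 3 both begin with "V 2 Randomization & 1 st Dose" on day 1, label a second dose at V3 (week 5) and a third at V4 (week 12), and mark study medication at those three visits only.

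**Visit dates.** Protocol 6.1, directly below the table, dates Visit 3 as Day 4 and Visit 4 as Day 7, and ends with Visit 6 at Day 28. SAP 7.1 bases the primary analysis on "comparing mean difference from Visit 1 to Visit 4".

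**Drug name.** Protocol 4.4, the Protocol abstract and SAP section 3 call the supplement 25-hydroxyvitamin D, which is the serum metabolite being measured. Protocol 4.7 says cholecalciferol.

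**Related sentences in 4.7.** "All participants will be treated with vitamin D supplements (Annexure attached"; vitamin D and calcium are supplied "according to the study (Annexure attached) on a weekly basis"; and "After screening further dose of RDA Vitamin-D will be provided for next 5 weeks to complete 24 weeks of study".

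**The concern.** This is not a criticism of the regimen. The difficulty is that the text does not say consistently what the regimen is. Strength and number of doses define the study drug, and each has two incompatible values.

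If dosing is still to come, a syringe filled to the milligram figure would hold four times the IU figure, and staff following 4.4 would dose weekly instead of at three visits. Under Protocol 4.5 and 4.6 the pharmacy supplies coded, identical 1 ml syringes to blinded staff, so nobody in the clinic could notice a strength error. Neither schedule table has a serum calcium row.

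If dosing is complete, the risk is that the regimen is reported wrongly. SAP 6.2 points that way, since it gives arm totals of 47 and 48 in the past tense.

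The visit dates are a separate defect. They matter because Visit 4 is the visit that supplies the follow-up value for the primary comparison.

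**Working it through.** **Inputs.** 100,000 IU and 10 mg (Protocol 4.7); weekly for 12 weeks (Protocol 4.4); doses on day 1 and at weeks 5 and 12 (both schedule tables); Visit 3 = Day 4, Visit 4 = Day 7, last visit = Day 28 (Protocol 6.1). Assumption from outside the documents: 1 IU vitamin D3 = 0.025 microgram.

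**1. Strength.** The plan's own figure is 100,000 IU = 10 mg. It does not reproduce.
- mg = IU × 0.025 / 1,000, so 100,000 × 0.025 / 1,000 = 2.5 mg.
- In reverse, 10 mg = 10,000 microgram, and 10,000 / 0.025 = 400,000 IU.
- Ratio: 10 / 2.5 = 4.
- For the printed pair to agree, one IU would have to be 10,000 / 100,000 = 0.1 microgram, four times the standard factor.

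**2. Total over the three tabulated doses.**

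| Figure taken as correct | Per dose | Three doses |
|---|---|---|
| IU | 100,000 IU (2.5 mg) | 300,000 IU (7.5 mg) |
| mg | 400,000 IU (10 mg) | 1,200,000 IU (30 mg) |

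**3. Number of administrations.** Section 4.4: one per week × 12 weeks = 12. Both tables: 3. The weeks 5 and 12 in 4.7, counted from initiation, fit the tables if initiation is the day 1 dose, although 4.7 does not restate that dose.

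**4. Visit timing.** The tables do not define how weeks are counted, so two conventions are shown.

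| Visit | Table time | Week n = days 7(n−1)+1 to 7n | n full weeks after Day 1 | Date in 6.1 | Gap |
|---|---|---|---|---|---|
| 3 | week 5 | Day 29 to 35 | Day 36 | Day 4 | 25 to 32 days |
| 4 | week 12 | Day 78 to 84 | Day 85 | Day 7 | 71 to 78 days |

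The gaps are roughly 4 weeks and 10 to 11 weeks. On either convention the last visit in 6.1 (Day 28) falls before week 5, and a Visit 4 on Day 7 would precede two of the three doses.

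**5. RDA phase.** Five weeks ending at week 24 would start at about week 24 − 5 = 19. The tables mark RDA only at V5 (week 24), and the arm is not stated.

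**The case against.** The best defence is that two things were given: a weekly supply and separate large doses at visits. Section 4.7 does mention vitamin D and calcium weekly and twice cites an attached annexure. The only annexure in the supplied text is a list of abbreviations, so one with dosing detail may exist elsewhere. This does not remove the conflict, because 4.4 puts placebo on the same weekly schedule and is therefore describing the randomised product. It does mean that the weekly wording in 4.4 should not be overwritten until the sponsor confirms the frequency as well as the strength. An annexure with the right dose would still leave the two figures in 4.7 disagreeing.

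Three further objections have force. The SAP's own table puts Visit 4 at week 12 and the SAP contains no Day 7 visit, so a reader who infers that the primary comparison is set at Day 7 goes too far. Section 6.1 lists no dose at Visits 3 or 4, so it is a conflicting calendar and not another regimen. The past tense in SAP 6.2 suggests that dosing may be over, which moves the weight from prevention to accurate reporting.

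The conversion factor is not in the documents. It is a unit definition, declared here as an assumption.

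**Conclusion.** The point stands and should be corrected. In the supplied text the single numeric dose is stated in two units that differ four-fold, given 1 IU = 0.025 microgram. The randomised product has 12 administrations in Protocol 4.4 and 3 in both tables. Separately, Protocol 6.1 places Visits 3 and 4 roughly 4 and 10 to 11 weeks earlier than the tables do.

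Several stronger readings are tempting but unsupported:
- *A wrong strength was dispensed.* No document shows this, or which of the IU and mg figures is the error.
- *Exposure is uncertain 16-fold.* This multiplies the two four-fold gaps (4 × 4). They are separate discrepancies, and no section describes twelve doses at the milligram strength.
- *The control arm received vitamin D.* The sentence about all participants conflicts with the placebo-plus-ART control in the abstract, the Performa and SAP section 3, and is probably a slip for ART. The weekly supply may follow allocation. Both are queries.
- *The RDA phase disturbs the vitamin D measurement.* Neither table schedules a vitamin D sample at Visit 5, so no such effect can be claimed. Which arm receives RDA, and in which weeks, is also a query.

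**What to change.** 1. **Confirm first.** Check the pharmacy preparation sheet, the annexure cited in 4.7 and, if dosing has occurred, the dispensing records. Establish both the strength and the number of doses.
2. **If 100,000 IU and three doses are confirmed**, write in 4.7: *Intervention arm: 100,000 IU (2.5 mg) cholecalciferol on day 1 and at weeks 5 and 12. Control arm: matching placebo oil at the same visits.* Put the same wording in 4.4 in place of the weekly schedule, and name the drug there as cholecalciferol instead of 25-hydroxyvitamin D. If something else is confirmed, state that consistently in 4.4, 4.7 and both tables.
3. **If a weekly vitamin D and calcium supply was also given**, describe it separately, by arm and with amounts.
4. **In 6.1**, replace the Day 4, 7, 14 and 28 calendar with the visit times in the table, and say how weeks are counted.
5. **Sponsor queries.** Does the sentence about all participants mean ART? Which arm receives RDA vitamin D, and in which weeks?
6. **If dosing is complete**, report the strength and number of doses actually given.

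The cost is amended wording in three sections and a check of pharmacy documents, plus a review of dispensing records by arm if dosing has taken place. No patient procedures are added.
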